23.0 Setting

This research is being conducted at the PRIDE Health Research consortium at Hunter College, New York, NY. All research procedures will be performed in the offices of the research facility.

Potential Participants are identified through healthcare provider referrals (e.g., Ryan White clinic or ATN clinic referrals), online social media, and dating apps. Please see recruitment sections for more information.

The Community Advisory Board for this protocol is a part of the national Youth Community Advisory Board for the Scale It Up program of research. They meet on a quarterly basis via skype to discuss study progress, recruitment strategies, and recommendations for youth engagement.

Sub-study:

Potential subjects are identified through the pool of subjects that screened ineligible for ATN 144 SMART or those who were not able to complete the study components to be enrolled in the SMART trial. These subjects were recruited from healthcare provider referrals (e.g., Ryan White clinic or ATN clinic referrals), online social media, and dating apps. Please see recruitment sections for more information. PRIDE Health Research Consortium at Hunter College, New York, NY, will perform all research procedures, excluding quantitative analysis of VL (to be performed by a third party lab) and the study data analyses to be performed by the Wayne State University Team in the offices of the research facility.

PROTOCOL TITLE: ATN 144 SMART

The Community Advisory Board for this protocol is a part of the national Youth Community Advisory Board for the Scale It Up program of research. They meet on a quarterly basis via skype to discuss study progress, recruitment strategies, and recommendations for youth engagement.

24.0 Resources Available

A number of recruitment strategies previously utilized by the Hunter College will be implemented by the Scale It Up REC. To ensure the desired sample of 120 participants is reached, both site referrals and national media campaigns will be used. The following are methods through which recruitment will take place: (1) referrals from Scale It Up clinical subject recruitment venues (SRVs), (2) social media ad campaigns, (3) geosocial networking data application ads, (4) nationwide flyers and recruitment material distribution, and (5) indirect recruitment through Hunter College's OMS.

The duration of this study is 43 months. During Months 1-4, the research team will focus on finalizing protocols, hiring/training staff, and completing IRB-related documents. For Months 5-19, the REC will recruit and enroll participants. After closing recruitment and enrollment, Months 20-31 are dedicated to completing the follow-up assessments. Finally, Months 32-43 are devoted to data analyses and dissemination.

Hunter College's Promoting Resilience, Intersectionality, Diversity, and Equity in Health Research Consortium was created to serve as a hub for Hunter's expanding work in sexual and gender minority health and broader focus on sexuality, gender, and health. The PRIDE Consortium supports research at the nexus of psychology, public health, and the health and helping professions that is relevant to understanding and addressing the health needs of diverse SGM individuals. A major focus of studies supported by the PRIDE Consortium has been to understand the structural, social, and psychological determinants of health disparities for SGM communities and to design and implement empirically-supported interventions to reduce disparities in the pursuit of health equity. The research center is located in midtown Manhattan and all services are research-related; no clinical services are provided at PRIDE.

Since this is a nation-wide study, youth needing more intensive assistance (medical or psychological) will be referred to their care team using the information provided on the participant's locator form, and with the youth's permission, the AF will contact the care team to share the concerns. Any adverse events reported by the participant to the AF will be triaged by the REC Clinical Team and appropriate procedures will be followed.

The MPIs of Scale It Up, and the MC, maintain responsibility for the overall conduct and implementation of the study; the MC is also responsible for management of recruitment and retention including enrollment and retention. The REC will also be responsible for Data Management while the AC will be responsible for analysis and reporting. The Protocol Leads are responsible for scientific leadership and dissemination. Protocol meetings are held bi-weekly to keep all assisting personnel informed about the protocol

PROTOCOL TITLE: ATN 144 SMART

and its procedures. Moreover, Dropbox is utilized to facilitate the storage and sharing of study-related documents, which further informs protocol personnel about any updates to research procedures.

Sub-Study:

A number of recruitment strategies previously utilized by the Hunter College will be implemented by the protocol team. To ensure the achievement of the desired sample size of 50 subjects, the protocol team will contact all of ATN 144 SMART's ineligible subjects or those who did not fulfill the enrollment components. These subjects were recruited using the following methods (1) referrals from Scale It Up clinical SRVs, (2) social media ad campaigns, (3) geosocial networking data application ads, (4) nationwide flyers and recruitment material distribution, and (5) indirect recruitment through Hunter College's OMS.

The duration of this study is 17 months. During Months 1-5, the research team will focus on finalizing protocol, study instruments, identifying the central lab for analyzing DBS specimens, and completing IRB-related documents. For Months 6-11, the PRIDE Team will recruit and enroll subjects. In addition, Months 7-12 are also dedicated to data analyses and dissemination.

Hunter College's PRIDE Health Research Consortium was created to serve as a hub for Hunter's expanding work in sexual and gender minority health and broader focus on sexuality, gender, and health. The PRIDE Consortium supports research at the nexus of psychology, public health, and the health and helping professions that is relevant to understanding and addressing the health needs of diverse SGM individuals. A major focus of studies supported by the PRIDE Consortium has been to understand the structural, social, and psychological determinants of health disparities for SGM communities and to design and implement empirically-supported interventions to reduce disparities in the pursuit of health equity. The research center is located in midtown Manhattan and all services are research-related; no clinical services are provided at PRIDE.

The principal investigator of Scale It Up and the Protocol Leads maintain responsibility for the overall conduct and implementation of the study. The Management Core, as well as the Recruitment and Enrollment Center, are responsible for management of recruitment, enrollment, and retention. The Recruitment and Enrollment Center will also be responsible for programming surveys in Qualtrics and databases as well as protocol development, and IRB submissions while the Wayne State University Team will be responsible for data management and analysis. The protocol leads are responsible for scientific leadership and dissemination. Protocol meetings are held as necessary to keep all assisting personnel informed about the protocol and its procedures. Moreover, Dropbox is utilized to facilitate the storage and sharing of study-related documents, which further informs protocol personnel about any updates to research procedures.

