4.0 Study Intervention

Cell Phone Support. Each participant randomized to CPS will be assigned a lead and back up Adherence Facilitator (AF). At the time of study entry, the AF and the

PROTOCOL TITLE: ATN 144 SMART

participant will choose a start date and arrange a call time that is after their daily ART dosage time and within office hours. For those participants taking their medication after dinner/before bed, the AF will call in the morning to confirm they took their ART the night before. While the study allows flexibility in planning for the timing of taking the medication and the phone call that follows it based on the participant's schedule, the call time should be mutually agreeable to the AF and the participant. All calls must take place during the agreed upon time range.

Preferably, calls should begin the next Monday following the baseline visit and/or within two weeks of study entry. Calls from the AF will occur Monday through Friday, once a day, and continue for three months, except for major holidays. While the initial call will last 10-15 minutes, it is expected that most calls will last less than five minutes. AFs will take an additional five minutes to document the content of the call. To protect the confidentiality of the participant, the AF will confirm that the person who answered the cell phone is the participant enrolled into the study. Voice recognition can be used as the primary confirmation; however, participants will also be offered the use of a code word for identification purposes to further protect their privacy. AFs will use cell phones to conduct the daily calls, send/receive texts, and have voice messages

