All responders will be randomized into the tapered intervention arm or into standard care, where no interventions (calls or texts) will be made. Those originally in the CPS group will receive the CPS tapered (CPS-T) intervention; likewise, those in the SMS group will receive the SMS tapered (SMS-T) intervention. In the tapered interventions, calls and texts will be reduced to two days a week. CPS-T and SMS-T will last for three months until the six month follow-up, after which participants will go into standard care. At this point, all responders will be in standard care, and will continue throughout the nine- and twelve-month follow-ups.

Participants who were non-responders after the first three months will be re-randomized to CPS or SMS, but with the addition of an incentive. They will receive incentives for text messaging or cell phone support participation. Those participants who answer the cell phone support call or respond to the text messages 75% of the time or more each month will receive an additional \$50 during the incentive phase. This will be implemented for three months until the six month follow-up, after which the intervention will be tapered to two times per week. Those in CPS-I will enter CPS-T, and those in SMS-I will enter SMS-T. After the nine-month follow-up, participants will enter standard care until completion of the study at the last twelve-month follow-up.

The three-, six-, nine-, and twelve-month follow-up assessments for all participants include a viral load and a computerized survey.

Sub-Study:

Project DABS does not implement any interventions.

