14.0 Risks to Subjects*

The SMART Protocol Team has determined that this study does not involve greater than minimal risk (45 CRF Part 46.404 and 21 CFR Part 50.51). Participation in this study does not involve any physical risk above and beyond that which would ordinarily be

PROTOCOL TITLE: ATN 144 SMART

encountered in daily life, standard clinical practice, or physical or psychological evaluations and tests. However, there is some risk of emotional discomfort or distress due to the personal nature of some questions asked in behavioral assessments as well as by the AF during intervention phone calls and risk of breaching confidentiality during the calls or text messages. Feedback from the AF is designed to be very respectful, but there is a chance that the AF and the participant may find parts of the phone calls distressing. Participants will be informed that they are free to decline to answer any questions, or withdraw from participation at any time without penalty. AFs will make every effort to ensure that the person who answers the cell phone is the participant enrolled into the study. This will be primarily conducted through voice recognition. If requested by the participant, the use of a code word can also be employed.

The HIV VL measurement will be collected for participants who do not have a record of a VL result obtained within the specified timeframes. The collection requires venipuncture to collect blood samples. This procedure may cause local discomfort, bleeding, or bruising; rarely small clot or infection can occur at the blood draw site. This measurement should not be considered greater than minimal risk in and of itself given its routine use in general health care delivery.

Sub-Study:

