17.0 Provisions to Monitor the Data to Ensure the Safety of Subjects*

This research involves no more than Minimal Risk to subjects.

The protocol has a Data Safety Monitoring Plan and is reviewed semiannually by a Study Monitoring Committee.

The Scale-It-Up (SIU) U19 Data Safety and Monitoring Plan will utilize a single monitoring system for all SIU protocols (including SMART) in order to harmonize review standards across protocols. The review process of the most vulnerable protocol will be applied to all SIU protocols thereby ensuring adequate oversight. We propose utilizing an independent study monitoring committee (SMC). A SMC was selected as the Clinical Research Management (CRM) as it is the highest level CRM needed for the most vulnerable SIU protocol. The proposed SMC will be composed of three independent experts who possess the relevant expertise (e.g., HIV-related research and prevention, adolescent medicine, and sexual health) to evaluate each SIU protocol and whom do not have a conflict of interest. [name], [name], and [name] have formally agreed to serve on the SIU SMC. Together, they represent an academically diverse and highly experienced team capable of providing the necessary foresight and oversight to ensure data safety monitoring plans are diligently designed and implemented. SIU has the appropriate funding available to financially support the activities of the SMC. The SMC will review each research protocol and plan for data and safety monitoring every 6 months, with additional ad-hoc reviews as necessary. All SMC meetings and reviews will be held via telephone conference.

Adverse Events Reporting. Data for monitoring participants' safety will be captured within the Access database as part of the required study data. There are no additional study-specific reporting requirements. Information on unexpected events including serious adverse effects will be reported to the sIRB.

Sub-Study:

This study does not involve more than minimal risk to subjects.

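### Clinical triage is described only for adverse events told to the adherence facilitator, and no harm question common to all arms is described, so harms may be ascertained unequally by arm

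*Protocol*

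**What the plan says.** **Route to triage.** Protocol 24.0 (Resources Available): "Any adverse events reported by the participant to the AF will be triaged by the REC Clinical Team and appropriate procedures will be followed". No other sentence describes how a participant's event comes to clinical attention at the Recruitment and Enrollment Center (REC).

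**Destination.** Under Protocol 17.0, data for monitoring participants' "safety will be captured within the Access database as part of the required study data". It then says "There are no additional study-specific reporting requirements" and "Information on unexpected events including serious adverse effects will be reported to the sIRB". On oversight by the Study Monitoring Committee (SMC): "The SMC will review each research protocol and plan for data and safety monitoring every 6 months".

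**Named risk.** Protocol 14.0 lists emotional distress and "risk of breaching confidentiality during the calls or text messages".

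**Who has an AF.** Protocol 4.0 assigns a lead and a back-up AF to participants randomized to CPS, with one call each weekday for three months. SMS participants arrange their messages with the Project Coordinator (Protocol 5.0) and then reply by text on whether they took their medication (Protocol 4.0). At month 3, responders are randomized to a taper or "into standard care, where no interventions (calls or texts) will be made". Non-responders from either arm are randomized to CPS or SMS with incentives, so some SMS starters acquire an AF then.

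**The concern.** The described intake route depends on a person whom one first-stage arm is due to speak to every weekday and the other is not due to speak to at all. It is also passive: no section gives an adverse-event definition, an elicitation question, a form or a schedule that applies to everyone.

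Two things are at stake. First, the risk named for text messages has no described means of detection in the arm that receives daily texts. The protocol itself treats disclosure as serious: its case for waiving parental permission (Protocol 10.0 and 22.0) rests on the possibility of harassment, abuse or expulsion from the home. Second, if the SMC is shown events by arm, few reports from SMS could reflect fewer harms or fewer chances to report them, and the data would not tell these apart.

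**Working it through.** The documents state no adverse-event rate, count or comparison, so there is no figure of the plan's own to reproduce. The check has three steps.

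**1. Could another contact fill the gap?**

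| Contact | Reaches | Described as asking about study harms or feeding triage? |
|---|---|---|
| AF calls (4.0, 24.0) | CPS, CPS-I, CPS-T | Volunteered reports are triaged |
| Project Coordinator set-up (5.0) | SMS | No |
| SMS replies (4.0) | SMS | No; medication taken or not |
| Reminder calls and texts (5.0) | All | No; logistics and locator form |
| Survey, including PHQ-8, GAD7 and HIV stigma (5.0) | All | No alert or study-harm instrument listed |
| Death notification (13.0) | All | Deaths only, direct to the REC |
| Access database, ethics board (17.0) | All | Destination only; no source stated |

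**2. How many participants have AF calls?**

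Inputs:
- N = 120 (Protocol 11.0; SAP 1.2.4), allocated 1:1 (Protocol 16.0; SAP 1.1), so 60 per arm.
- Responder rate p = 0.5 (Protocol 16.0, Sample Size and Power), varied over 0.4 to 0.7 (SAP 1.2.4 power table), equal in both arms as SAP 1.2.4 assumes.
- Second randomization 1:1. This is an assumption; the ratio is not stated.

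In stage 1, planned AF coverage is 60 × 3 = 180 of 180 person-months in CPS and 0 of 180 in SMS, whatever the responder rate.

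Over the whole trial, an SMS starter has AF calls only as a non-responder randomized to CPS-I:
- SMS starters ever having AF calls = 60(1 − p)/2
- share never having them = 1 − (1 − p)/2 = (1 + p)/2

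| p | SMS non-responders | Move to CPS-I | Never have AF calls | Share never | All participants ever having AF calls |
|---|---|---|---|---|---|
| 0.4 | 36 | 18 | 42 | 70% | 78/120 = 65% |
| 0.5 | 30 | 15 | 45 | 75% | 75/120 = 62.5% |
| 0.6 | 24 | 12 | 48 | 80% | 72/120 = 60% |
| 0.7 | 18 | 9 | 51 | 85% | 69/120 = 57.5% |

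Protocol 5.0 counts a missing month-3 viral load as non-response, which could push the working p below 0.4. Since (1 + p)/2 is at least 0.5, at least half of SMS starters would still never have AF calls.

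Standard care from month 3: 60p/2 enter from each arm, that is 15 and 15 at p = 0.5. Half of them therefore had three months of AF calls beforehand. None has AF calls while in standard care.

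**3. What could unequal capture do?**

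This step is illustration only; every rate is assumed. With the same true three-month risk r in both arms and capture probability c, expected recorded events = 60 × r × c. Take r = 0.10 and c = 0.80 in CPS: 60 × 0.10 × 0.80 = 4.8. In SMS, c = 0.80, 0.40, 0.20 or 0 gives 4.8, 2.4, 1.2 or 0. The apparent ratio equals the ratio of the capture probabilities, and the documents give neither.

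**The case against.** The case on the other side is substantial.

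- **A reader might infer that the AF is the sole permitted route.** The sentence sits in a resources section and says what happens to events told to the AF; it excludes nothing else. Protocol 17.0 is the governing section, and its capture and reporting statements are not limited by arm. Deaths go straight to the REC. Protocol 17.0 also relies on a network-wide Data Safety and Monitoring Plan that is not among the documents, and consent pages were removed, so reporting instructions may exist elsewhere. This stands: the finding concerns what is described.
- **A reader might infer that most standard-care participants never speak to an AF.** That is wrong. About half of those randomized to standard care come from CPS.
- **A reader might turn AF coverage into an event-rate ratio.** At p = 0.5, with 15 per trajectory, CPS starters have 15 × (3 + 6 + 9 + 3) = 315 of 720 person-months with AF calls and SMS starters 15 × 6 = 90 of 720. That is a ratio of 3.5, with 405 of 1,440 (28%) overall. These figures describe coverage. They become a bias in event rates only if nothing is captured outside AF contact and nothing is reported later, which the documents do not say.
- **Texts are not unprotected.** SMS participants choose timing and wording, and the delivery platform is described as encrypted (Protocol 4.0). Sole ownership of the device is required (Protocol 9.0). These measures reduce the chance of a breach; they do not detect one.
- **Distress is measured alike in all arms** by PHQ-8 and GAD7. This allows a symmetric comparison of psychological state, but it does not capture disclosure and no clinical alert is described.
- **The study is classed as minimal risk, and no between-arm adverse-event analysis is planned** in Protocol 16.0 or the SAP. No by-arm event table for the SMC is described either. This limits the severity.

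What remains is that no elicitation is common to all arms, that routing of reports made to staff other than the AF is unstated, and that AF contact differs sharply by arm.

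**Conclusion.** The point holds as a gap in harm ascertainment. The protocol describes clinical triage only for events volunteered to the AF and specifies no question, form or schedule common to all arms. Planned AF contact in stage 1 is complete in CPS and absent in SMS. About 75% of SMS starters never have AF calls (70% to 85% for responder rates of 40% to 70%), assuming a 1:1 second randomization and equal responder rates.

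Harms from text messages may go undetected, and any event counts by arm that reach the SMC are open to ascertainment bias. The documents do not support saying that such harms will go unseen or that safety cannot be compared at all: capture outside AF contact is unknown, so the bias cannot be sized. In a minimal-risk trial with no planned safety comparison, this is a worthwhile and inexpensive improvement. It does not bear on the efficacy analysis.

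**What to change.** 1. Add two or three identical items to the existing computer-assisted survey at months 3, 6, 9 and 12 for every participant, whatever the arm or stage: whether anyone learned their HIV status through study calls, texts or emails; distress from study contact; any other harm they attribute to the study.
2. Send positive answers to the existing REC Clinical Team, for example by an automatic survey alert.
3. Reword the sentence in Protocol 24.0 so that triage covers events reported to any study staff member or in the survey. Reconcile it with Protocol 17.0 by stating who enters events in the Access database and from which sources.
4. Show the SMC survey-elicited events by arm, separately from volunteered events. The elicited counts come from the same question on the same schedule in each arm, so they are the ones to compare; survey completion by arm should be shown beside them.

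Cost: a slightly longer survey, some extra triage and a minor amendment. Randomization, visit schedule and efficacy analyses are unchanged.
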